2.1.1 Pharmacokinetic (PK) analysis set

This analysis set comprises all patients who received at least 1 dose of benralizumab and from whom PK blood samples are not assumed to be affected by factors such as protocol violations

(Section 2.2) and who had at least one quantifiable serum PK observation post first investigational product (IP) dose.

2.1.2 Non-compartmental analysis (NCA) set

This analysis set comprises all patients who received the first dose of benralizumab and from whom PK blood samples are not assumed to be affected by factors such as protocol violations (Section 2.2) and who had at least 3 quantifiable serum PK observations post-dose on Days 1, 7, 14, and 28.

2.1.3 Safety analysis set

This analysis set comprises all patients who receive at least one dose of benralizumab. All safety and PD analyses will be based on safety analysis set.

2.2 Violations and deviations

Important protocol deviations (IPDs) are considered any protocol deviation that may greatly impact the completeness, accuracy, and/or reliability of the study data or that may significantly affect a patient's rights, safety, or well-being. They may include (but not be limited to):

- Patients who were assigned to a study treatment even though they did not meet key entry criteria
- Patients who developed withdrawal criteria during the study but were not withdrawn
- Patients who received the wrong treatment or an incorrect dose
- Patients who received a restricted or prohibited concomitant treatment.

Only IPDs will be listed and tabulated in the clinical study report (CSR). All the IPDs will be identified and documented by the study team prior to database lock.

IQVIA will prepare a separate protocol deviation Analysis Set Plan document to facilitate the identification of all IPDs to be documented prior to DBL. All the identified IPDs will be collected via the Clinical Trial Management System (CTMS) log. Any protocol deviation which are not defined as important will not be reported or discussed in the CSR. Subjects excluded from the PK set will be listed.

3 PRIMARY AND SECONDARY VARIABLES

3.1 General Principles

3.1.1 Baseline definitions

In general, the last non-missing measurement prior to the first dose of study treatment will serve as the baseline measurement. If there is no value prior to first dose of study treatment,

then the baseline value will not be imputed, and will be set to missing.

The screening clinical chemistry and haematology samples collected at Visit 1 (Day -28 to Day -14) will be used as baseline. However, if Visit 2 (Day 0) is done > 28 days after Visit 1, then the corresponding clinical chemistry and haematology samples collected at Visit 2 and prior to the first dose of study treatment, will be used as baseline.

The PK sample collected on the same day but at a time prior to the first dose of study treatment (Visit 2) will be included in the baseline definition. If there is no PK sample value prior to the first dose of study treatment, then the baseline value will not be imputed and will be set to missing. If the PK sample prior to the first IP is below the lower limit of quantification (LLOQ) then the baseline will be set to zero.

For physical examination and vital signs, baseline will be defined as the latest non-missing assessment prior to first dose at Visit 2. If no time is recorded for an assessment, and the assessment takes place at Visit 2, this will be assumed to be a pre-dose assessment.

3.1.2 Study day

Whenever data are summarised over time, study day will be calculated based on the actual assessment date, and is defined as:

Study day = Date of assessment – date of first dose of study treatment.

Study day 0 is defined as the date of the first dose of study treatment.

3.1.3 Study Periods

The following study periods are defined for analysis purposes:

- Pre-Treatment (Screening period): starting on the date of the first study procedure and ending one day prior to date assigned study treatment (for subjects assigned study treatment) or on the date of the last study procedure (for screening failures). If any subject is re-screened, the latest available screening will be used for this purpose.
- On-treatment period: defined as starting between day of first dose of study treatment and scheduled end of treatment (EOT) visit or early discontinuation (DXD) visit for those patients who prematurely discontinue study treatment, inclusive. If both EOT and DXD visits are missing then the upper limit of the on-treatment period is defined as the day of last dose of study treatment + 56 days. If the upper limit is after the end of on-study period, then the upper limit is end of on-study period
- On-study period: starting on the date of first dose of IP and ending on the study completion or withdrawal date

3.1.4 Visit windows

Table 1 of the CSP detailed the time points and visit window for the study assessments. All summaries which are presented by time point will use a visit window to classify the data record, which is derived from the assessment date relative to the reference start date (date of first dose of study treatment). This approach allows appropriate classification of visits which may have occurred significantly earlier or later than the protocol assessment schedule, as well as the use of data captured at visits which have no fixed timing.

Inclusion within the visit window should be based on the actual date and not the intended nominal date of the visit.

Any data collected at unscheduled or repeat visits will be listed, and will be included in baseline definitions (Section 3.1.1), and in any definitions of maximum value, minimum value or last value within the relevant study period.

Data collected at unscheduled or repeat visits will also be included in visit windows, and therefore may be included in summaries by visit. In the case of a missing value at a scheduled visit, which is then followed by a non-missing value at an unscheduled or repeat assessment within the same visit window, the non-missing value at the unscheduled/repeat assessment will replace the missing value at the scheduled visit.

If a subject has more than one non-missing value within the same visit window, the following rules will apply:

- The non-missing value closest to the target day will be selected for analysis at that visit
- If two non-missing values are the same distance from the target day, the earlier of the two values will be selected for analysis at that visit
- If two non-missing values are recorded on the same day and have a different assessment time associated with both of them, the value with the earliest assessment time will be selected for analysis at that visit.
- If two non-missing values are recorded on the same day and have no assessment time associated with at least one of them, or the same assessment time associated with both of them, the average of the two values will be selected for analysis at that visit.
If a subject has no value within a particular visit window, then the subject will have a missing value at that visit in summaries.

Due to the overlap in the week 1 and 2 visit window schedule of assessments the following rules will apply subject to the above rules described in this section above:

- If Week 1 timepoint has only one record within analysis days 3-10 then this will be assigned to the Week 1 analysis visit, as described above.
- If Week 1 timepoint has multiple records (with evaluable results) within analysis days 3-10 then:

- a) if the latest record (using time) has analysis day = 10, then this record will be considered for selection within the Week 2 analysis visit, subject to the existing rules described in this section above, and
- b) all earlier records within analysis days 3-10 will be considered for selection within the Week 1 analysis visit, subject to the existing rules described in this section above

For PK measures, if there are 2 samples from the same date, the value from the scheduled visit will be used. If the scheduled visit is missing, then the record from the unscheduled visit will be used. If the sampling times are different, both PK samples will be transferred to database and used in population PK (PopPK) analysis.

Blood samples for determination of PK parameters in serum will be taken at timelines as specified in Table 1 of CSP. Blood samples taken at visits when a dose of benralizumab is administered must be taken pre-dose. Blood samples taken at visits when no benralizumab dose is administered may be taken at any time during the day of the visit. The time and date of blood samples taken for PK analysis must be recorded on the eCRF

For PK serum concentration-time data, any post-dose samples taken outside the window from scheduled time point will be excluded from the summary tables and figures.

The adjusted analysis-defined windows will be based on the collection schedule listed in the protocol and variables will be windowed to the closest scheduled visit for that variable.

Visit windows following baseline will be constructed in such a way that the upper limit of the interval falls halfway between the two visits (the lower limit of the first post-baseline visit will be study day 1). If an even number of days exists between two consecutive visits then the upper limit will be taken as the midpoint value minus 1 day. Visit windows are constructed so that every observation collected can be allocated to a visit ([Table 1](#)). No visit windows will be defined for screening visits.

Table 1: Visit windows for assessments

Timepoint Target	Day	Visit Window							
		AE, CM, Asthma Exac and VS	PK sampling	ACQ-IA	Clinical chemistry, Haematology , Serology, Urinalysis, and FEV1	Brief PE	ADA,	PGIC- IA and CGIC	Height and Weight
Baseline	0	See section 3.1.1 for baseline definitions							
Week 0 day 0									
Week 0 day 1	1	1-2	1-2						
Week 1	7	3-10	3-10	1-10					
Week 2	14	11-20	11-20	11-20					
Week 4	28	21-41	21-41	21-41	1-41	1-41			
Week 8	56	42-69	42-69	42-69	42-69	42-69	1-83		
Week 12	84	70-97	70-97	70-97	70-97	70-97			
Week 16	112	98-139	98-139	98-139	98-139	98-139	84-139	1-139	1-139
Week 24	168	140-195	140-195	140-195	140-251	140-195	140-195	140-195	140-251
Week 32	224	196-251		196-251		196-251		196-279	
Week 40	280	252-307		252-307		≥252			
Week 48	336	308-348	308-348	308-348	≥252		308-348	≥280	≥252
Follow-up (Week 52)	362	≥349		≥349					

Abbreviations: ACQ-IA interviewer-administered asthma control questionnaire, ADA anti-drug antibody(ies), PGIC-IA interviewer administered patient global impression of change, PK pharmacokinetics, VS vital signs, AE adverse events, CM concomitant medication, ACQ-IA interviewer-administered asthma control questionnaire, Exac Asthma exacerbation, PE Physical examination, ECG electrocardiogram.

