|---------------------|--------------------------------------|--|--|
| 15-20 | 1200-1600 | 12.0-16.0 | 36.0-48.0 |
| 21-25 | 1680-2000 | 16.8-20.0 | 50.4-60.0 |
| 26-30 | 2080-2400 | 20.8-24.0 | 62.4-72.0 |
| 31-35 | 2480-2800 | 24.8-28.0 | 74.4-84.0 |
| 36-40 | 2880-3200 | 28.8-32.0 | 86.4-96.0 |
| 41-45 | 3280-3600 | 32.8-36.0 | 98.4-108.0 |
| 46-50 | 3680-4000 | 36.8-40.0 | 110.8-120.0 |
| 51-55 | 4080-4400 | 40.8-44.0 | 122.4-132.0 |
| 56-60 | 4480-4800 | 44.8-48.0 | 134.4-144.0 |
| 61-65 | 4880-5200 | 48.8-52.0 | 146.4-156.0 |
| 66-70 | 5280-5600 | 52.8-56.0 | 158.4-168.0 |
| 71-75 | 5680-6000 | 56.8-60.0 | 170.4-180.0 |
| 76-80 | 6080-6400 | 60.8-64.0 | 182.4-192.0 |

Table 6 Maximum volume of blood to be withdrawn from a patient

| Patient weight (kg) | Total blood volume (mL) ^a | Maximum blood volume (mL) to be withdrawn at any visit | Maximum blood volume (mL) to be withdrawn within a 4-week period |
|---------------------|--------------------------------------|--|--|
| 81-85 | 6480-6800 | 64.8-68.0 | 194.4-204.0 |
| 86-90 | 6880-7200 | 68.8-72.0 | 206.4-216.0 |
| 91-95 | 7280-7600 | 72.8-76.0 | 218.4-228.0 |
| 96-100 | 7680-8000 | 76.8-80.0 | 230.4-240.0 |

^a The total blood volume is estimated at 80 mL/kg body weight.

Source: [EMA 2008](#)

The total maximum volume of blood that will be withdrawn from each patient at each study visit is listed in Table 7.

Table 7 Maximum volume of blood to be withdrawn from each patient

| Visit | Samples required | Total maximum volume (mL) ^a |
|-----------------------------|---|--|
| Visit 1 (Screening) | clinical chemistry; haematology; serology | 13.0 |
| Visit 2 | PK; ADA | 5.0 |
| Visit 3 | PK | 2.5 |
| Visit 4 | PK | 2.5 |
| Visit 5 | PK | 2.5 |
| Visit 6 | clinical chemistry; haematology; PK | 7.0 |
| Visit 7 | clinical chemistry; haematology; PK; ADA | 9.5 |
| Visit 8 | clinical chemistry; haematology; PK | 7.0 |
| Visit 9 | clinical chemistry; haematology; PK; ADA | 9.5 |
| Visit 10 | clinical chemistry; haematology; PK; ADA | 9.5 |
| Visit 11 | | 0 |
| Visit 12 | | 0 |
| Visit 13 (End of Treatment) | clinical chemistry; haematology; PK; ADA | 9.5 |
| Visit 14 (Follow-up) | | 0 |
| Early discontinuation (DXD) | clinical chemistry; haematology; PK; ADA | 9.5 |
| Total (mL) | | 87.0 |

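### SAP Table 1 breaks the SAP's own visit-window rule for anti-drug antibodies, so ADA samples on Days 196-307 and from Day 349 belong to no visit

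*SAP*

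**What the plan says.** SAP 3.1.4 gives the construction rule in words. Windows are specific to each variable: "variables will be windowed to the closest scheduled visit for that variable". On the limits it says "Visit windows following baseline will be constructed in such a way that the upper limit of the interval falls halfway between the two visits", and then "If an even number of days exists between two consecutive visits then the upper limit will be taken as the midpoint value minus 1 day". It adds that "Visit windows are constructed so that every observation collected can be allocated to a visit". The stated purpose of windowing includes "as well as the use of data captured at visits which have no fixed timing", which describes the early discontinuation (DXD) visit.

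The sampling schedule is clearest in Protocol section 8, Table 7. ADA is taken at Visits 2, 7, 9, 10 and 13 and at DXD. The Week 24 entry reads "Visit 10 | clinical chemistry; haematology; PK; ADA | 9.5". Visits 11, 12 and 14 (Weeks 32, 40 and 52) take no blood.

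SAP Table 1 then prints the windows. Its columns run: AE/vital signs, PK, ACQ-IA, laboratory/FEV1, brief physical examination, ADA, PGIC/CGIC, height/weight. The Week 24 row is "Week 24 168 140-195 140-195 140-195 140-251 140-195 140-195 140-195 140-251". The Week 48 row begins "Week 48 336 308-348 308-348 308-348 ≥252" and gives ADA 308-348. The PK and ADA cells are blank at Weeks 32, 40 and 52.

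**The concern.** The text and the table give a programmer two incompatible instructions. Under the text, every ADA result after Week 16 falls in Week 24 or Week 48. Under the table, results on Days 196-307 or from Day 349 fall nowhere, and SAP 3.1.4 then sets the child to missing at that visit.

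The samples at risk come mainly from children who leave early. After a DXD visit, Protocol 7.1.1 requires only adverse events and concomitant medication, so the DXD sample may be the only ADA result that could represent Week 48. The same visit would also be handled inconsistently: on Day 290 the eosinophil count is windowed to Week 48 and the ADA result is not windowed at all. Protocol 9.5.4.2 plans ADA summaries at each visit and an assessment of ADA against eosinophil level.

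**Working it through.** **Inputs.** Target days 56, 112, 168 and 336 for post-baseline ADA (Protocol Tables 1 and 7; SAP Table 1). Rule from SAP 3.1.4: upper limit = (d1 + d2)/2, less 1 day when d2 − d1 is even; next lower limit = previous upper limit + 1; first lower limit = Day 1; last window open-ended.

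**Does the rule reproduce the table?** It reproduces every window in the ACQ-IA, laboratory/FEV1, PGIC/CGIC and height/weight columns. In the AE/vital-signs column it differs only at the Day 1/Week 1 boundary (rule 1-3 and 4-10, table 1-2 and 3-10), which leaves no gap. So the rule has been read correctly.

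**ADA column.**

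| Visit | Calculation of upper limit | Rule | SAP Table 1 |
|---|---|---|---|
| Week 8 | (56 + 112)/2 − 1 = 83 | 1-83 | 1-83 |
| Week 16 | (112 + 168)/2 − 1 = 139 | 84-139 | 84-139 |
| Week 24 | (168 + 336)/2 − 1 = 251 | 140-251 | 140-195 |
| Week 48 | last visit, open-ended | ≥252 | 308-348 |

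The laboratory/FEV1 and height/weight columns also go from Week 24 straight to Week 48, and they carry 140-251 and ≥252.

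The printed ADA limits are those that result when Weeks 32, 40 and 52 are scheduled visits: (168 + 224)/2 − 1 = 195; (280 + 336)/2 − 1 = 307, so the next window starts at 308; and (336 + 362)/2 − 1 = 348. ADA has none of those visits.

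**Unassigned days.** 307 − 196 + 1 = 112 days, plus every day from 349.

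**Which samples could fall there?** Protocol 7.1.1 places the DXD visit within 4 weeks of the last dose. On nominal dosing days:

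| Last dose | Possible DXD days | In the gap |
|---|---|---|
| Day 168 | 168-196 | 1 of 29 (Day 196) |
| Day 224 | 224-252 | 29 of 29 |
| Day 280 | 280-308 | 28 of 29 (Days 280-307) |

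**What would the rule-based windows recover?** Samples on Days 196-251 would join Week 24, where the value closest to Day 168 is selected, so an on-time Week 24 sample would win. New use at Week 48 is limited to Days 252-307 and Day 349 onward. After an on-time Day 224 dose, that is Day 252 only. If that dose is 7 days late (Day 231), the 4-week limit is 231 + 28 = Day 259. After the Day 280 dose it is Days 280-307.

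**End of treatment.** The protocol window is 336 ± 7 = Days 329-343, wholly inside 308-348. Only a sample on Day 349 or later, at least 349 − 343 = 6 days beyond the protocol window, is unassigned.

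**Weight of one child.** SAP 4.1 uses the number of patients in the treatment/weight group as the denominator. With the minimum stratum of 8, one positive result is 1/8 = 12.5 percentage points of a by-visit row. If the other stratum holds 30 − 8 = 22, it is 1/22, about 4.5 points.

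**The case against.** The strongest reply is that little depends on these rows, and most of it stands.

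- A reader might infer that a child's last immunogenicity result is lost. It is not. Under SAP 4.2.8, ADA prevalence, incidence, persistence and the neutralising-antibody categories use any post-baseline result or the last available one, and cross-visit titres use the maximum. None is defined by a window. ADA results are also listed, and ADA variables may only be listed if positives are few.
- A reader might take 112 of 336 days as the share of data at risk. No ADA sample is scheduled on those days, so the figure measures calendar time.
- Week 40 is the last dose, so after it no treatment remains to discontinue. Samples on Days 280-307 would come mainly from study withdrawals. Correcting the windows also recovers few discontinuation samples after the Week 32 dose.
- A reader might conclude that PK, with the same printed limits, needs the same correction. The documents do not support that. SAP 3.1.4 and 4.2.5.2 separately exclude out-of-window post-dose PK samples from tables and figures, so widening alone might change nothing. Concentration also depends on time since dose, so a gap could be deliberate. What remains is a conflict: SAP 4.2.5.2 admits DXD samples within one dosing cycle to the scheduled-visit summaries, while Table 1 gives those on Days 196-307 no visit to enter.
- The match with columns that do have Weeks 32, 40 and 52 suggests a cause, but the documents do not establish one.

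None of this removes the contradiction between text and table for ADA, and no SAP text explains an ADA gap.

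**Conclusion.** For ADA, SAP Table 1 contradicts both the midpoint rule and the completeness statement in SAP 3.1.4. The consequence is minor: some late samples are missing from the Week 48 by-visit row, and haematology and ADA from one visit are windowed differently. The haematology comparison assumes a DXD sample within one dosing cycle of the last dose, as SAP 4.2.6.1 requires for eosinophil summaries.

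The Day 0-28 PK parameters, the Week 16 trough, the population PK analysis and the eosinophil endpoint do not rest on these windows.

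The number of children affected cannot be derived from the documents; that it is small is an assumption. The 12.5 and 4.5 point figures assume one positive sample, the stratum size as denominator, and an 8/22 split of 30. For PK, the supported conclusion is that the provisions need reconciling.

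**What to change.** In SAP Table 1, set the ADA windows to 140-251 (Week 24) and ≥252 (Week 48).

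For PK, add a sentence to SAP 3.1.4 or 4.2.5.2 that reconciles Table 1 with the DXD inclusion rule and the out-of-window exclusion. It should say which visit, if any, samples on Days 196-307 and after Day 348 enter, or state that the gap is deliberate because concentration depends on time since dose.

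The cost is two table cells, one sentence and the matching programming change. No new data are needed.

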3.1.5 Handling of missing data

There will be no imputation for safety data.

Missing dates are not anticipated, except for concomitant medication dates. Medications with missing partial start date or end date such that it is not possible to classify as prior or concomitant will be considered as concomitant.

Details on the algorithm for handling medication and adverse event partial missing dates can be found in [Appendix I](#).

Details on the handling of missing PK data can be found in section [4.2.5.1](#)

3.2 Primary outcome variables

3.2.1 Primary PK variables

The primary PK outcome measure is the evaluation of benralizumab administered SC in children with severe eosinophilic asthma by assessing benralizumab concentrations versus time profile and the PK parameters derived.

The PK parameters to be determined are:

- Clearance
- AUC_{0-28}
- C_{max}
- $t_{1/2}$
- T_{max}

3.2.2 Primary PD variable

3.2.2.1 Blood eosinophil levels

Blood samples for determination of eosinophil count levels (haematology) will be taken at the time points detailed in Table 1 of the CSP and will be assessed in a central laboratory. Blood eosinophil counts levels will be evaluated at Screening (Visit 1, Day -28 to -14) and the change from baseline to Weeks 4, 8, 12 and 16 (Part A), and Weeks 24 and 48 (Part B) is the primary PD variable to evaluate the PD of benralizumab administered SC in children with severe eosinophilic asthma.

3.3 Secondary outcome variables

3.3.1 Body weight-adjusted clearance

Body weight-adjusted clearance parameter is one of the secondary variables that will be used to further assess the PK of benralizumab.

3.3.2 Immunogenicity Variable

Serum samples for the determination of ADA in serum will be taken prior to IP administration at the study visits indicated in CSP Table 1. Serum samples for ADA assessments will be conducted utilizing a tiered approach (screen, confirm, titre). ADA result from each sample will be reported as either positive or negative. If the sample is positive, the ADA titre will be reported as well. In addition, the presence of neutralizing antibody (nAb) will be tested in all ADA-positive samples using a ligand-binding assay. The nAb results will be reported as positive or negative. Details of the analytical methods used will be described in a separate validation report.

3.3.3 Pre-bronchodilator forced expiratory volume in first second (pre-BD FEV₁)

Change from baseline in pre-dose (when applicable), pre-bronchodilator, FEV₁ measured at Weeks 4, 8, 12, and 16 (Part A), and Weeks 24 and 48 (Part B) will be used as a secondary variable to evaluate the effect of benralizumab on pulmonary function.

The pre-BD FEV₁ will be measured by spirometry at the study centre.

Multiple forced expiratory efforts (at least 3 but no more than 8) will be performed for each centre spirometry session and the 2 best efforts that meet the American Thoracic Society (ATS)/ European Respiratory Society (ERS) acceptability and reproducibility criteria will be recorded in the eCRF. The best efforts will be based on the highest FEV₁. The absolute measurement (for FEV₁), and the percentage of predicted normal value will be recorded using the local spirometer at the site with predicted values derived from a reference value.

